7.8.1.1 Pre-specified adverse events of special interest

Gastrointestinal perforations and hepatic injury are adverse events of special interest (AESI) pre-specified in the CTP Section 5.3.7.1. These are investigator reported on the eCRF and will be identified using this information for this analysis.

The frequency of patients with pre-specified AESI will be summarised by treatment, primary SOC and preferred term (PT).

7.8.1.2 Adverse events with additional information collection

Diarrhoea and bleeding are AEs with additional AE-specific information collected on the eCRF. These are investigator reported on the eCRF and will be identified using this information for this analysis. That is if the diarrhoea information has been completed for an adverse event then the adverse event will be considered as diarrhoea for this analysis regardless of subsequent MedDRA coding of the verbatim term. Likewise, if the bleeding information has been completed for an adverse event then the adverse event will be considered as bleeding for this analysis regardless of subsequent MedDRA coding of the verbatim term.

The frequency of patients with AEs with additional information collection will be summarised by treatment, primary SOC and PT separately for diarrhoea and bleeding. The additional information collected will also be summarised at the AE level rather than at the patient level separately for diarrhoea and bleeding.

7.8.1.3 Adjudicated adverse events

An independent adjudication committee will review all fatal cases and adjudicate cause of death to cardiovascular death, respiratory related death, non-cardiovascular/non-respiratory death, or undetermined cause of death on a per patient basis, e.g. one cause per patient. The adjudication committee will also review all AEs categorised as MACE according to the definition in the adjudication charter.

In addition to standard safety analyses, the frequency of patients with AEs leading to death will be summarised by treatment, adjudicated cause of death (Cardiac, Respiratory, Non-cardiac/non-respiratory or Undetermined), and PT.

The frequency of patients with AEs categorised as MACE (that is all AEs with trigger terms for MACE and therefore sent for adjudication) will be summarised by treatment and outcome of adjudication (adjudicated as MACE or adjudicated as not MACE). The frequency of patients with AEs adjudicated as MACE will also be summarised by treatment and PT.

7.8.1.4 Additional analysis of adverse event groupings by system

Further adverse event groupings by system have been defined outside the trial protocol as medically relevant to the clinical development program and are specified in [Table 7.8.1.4: 1](#). The frequency of patients with AEs within these groupings will be summarised by treatment, safety topic and preferred term. Separate tables will be provided for patients with investigator defined drug-related AEs and serious AEs (SAEs).

Table 7.8.1.4:1 Adverse events by system and safety topic using aggregated terms

System	Safety Topic	Definition (selection criteria)
Gastrointestinal	Diarrhoea	PT Diarrhoea
	Nausea	PT Nausea
	Vomiting	PT Vomiting
	Abdominal pain	HLT 'Gastrointestinal and abdominal pains (excl oral and throat)
	Pancreatitis	SMQ Acute pancreatitis (narrow)
	Gastrointestinal perforation	SMQ Gastrointestinal perforation (narrow)
Hepatobiliary	Drug-induced liver injury (DILI)	PT Drug-induced liver injury
	Hepatic disorders combined Sub-categories: 
 • Drug related hepatic disorders – comprehensive search (SMQ narrow) • Liver related investigations, signs and symptoms (SMQ broad) • Cholestasis and jaundice of hepatic origin (SMQ narrow) • Hepatitis, non-infectious (SMQ narrow) 	Table to show cumulative row for all 4 SMQs below, followed by a cumulative row for each subSMQ, followed by all PTs driving that subSMQ SMQ Drug related hepatic disorders – comprehensive search (narrow) OR SMQ Liver related investigations, signs and symptoms (broad) OR SMQ Cholestasis and jaundice of hepatic origin (narrow) OR SMQ Hepatitis, non-infectious (narrow)
	Hepatic failure	SMQ Hepatic failure, fibrosis and cirrhosis and other liver damage-related conditions (narrow)

Table 7.8.1.4:1 Adverse events by system and safety topic using aggregated terms (cont'd)

System	Safety Topic	Definition (selection criteria)
Cardiovascular	Arterial thromboembolism	SMQ Embolic and thrombotic events, arterial (narrow)
	Myocardial infarction	SMQ Myocardial infarction (narrow)
	Stroke	Pharmacovigilance Endpoint Stroke PTs (see Section 9.7) for included Preferred Terms)
	Stroke haemorrhagic	SMQ Haemorrhagic central nervous system vascular conditions (narrow)
	Stroke ischaemic	SMQ Ischaemic central nervous system vascular conditions (narrow)
	Stroke haemorrhagic and ischaemic	SMQ Haemorrhagic central nervous system vascular conditions (narrow) OR SMQ Ischaemic central nervous system vascular conditions (narrow)
MACE	Sub-categories: 
 • Fatal events in SOC Cardiac disorders • Fatal events in SOC Vascular disorders • Any fatal or non-fatal events in SMQ Myocardial infarction (broad) • PTs Cardiac death, Sudden death, Sudden cardiac death • Any fatal or non-fatal stroke events 	Fatal events in SOC Cardiac OR Fatal events in SOC Vascular OR Any fatal or nonfatal events in SMQ Myocardial infarction (broad) OR PTs Cardiac death, Sudden death, Sudden cardiac death OR Any fatal or nonfatal events as defined in Pharmacovigilance Endpoint Stroke PTs – updated to MedDRA 21.0

Table 7.8.1.4:1 Adverse events by system and safety topic using aggregated terms (cont'd)

System	Safety Topic	Definition (selection criteria)
Cardiovascular	Cardiac failure	SMQ Cardiac failure (narrow)
	QT prolongation	SMQ Torsade de pointes/QT prolongation (narrow)
	Venous thromboembolism	SMQ Embolic and thrombotic events, venous (narrow)
	Pulmonary embolism	PT Pulmonary embolism
	DVT	PT Deep vein thrombosis
	Hypertension	SMQ Hypertension (narrow)
Metabolic	Decreased appetite	PT Decreased appetite
	Weight decreased	PTs: Weight decreased, Abnormal loss of weight
Blood	Bleeding Subcategories: 
 • GI bleeding – oral • GI bleeding – upper • GI bleeding – lower • GI bleeding – nonspecific • Skin bleeding • Respiratory bleeding • CNS bleeding • Urogenital bleeding • Other bleeding 	SMQ Haemorrhage terms (excl laboratory terms) (narrow) displayed in total and then according to categories (attached spreadsheet): 
 • Gastrointestinal – oral • Gastrointestinal – upper • Gastrointestinal – lower • Gastrointestinal – nonspecific • Skin • Respiratory • CNS • Urogenital • Other
	Thrombocytopenia	PTs: Thrombocytopenia, Platelet count decreased, Immune thrombocytopenic purpura
	Haematopoietic thrombocytopenia	SMQ Haematopoietic thrombocytopenia (broad)
	Neutropenia	SMQ Agranulocytosis (narrow) OR SMQ Haematopoietic leukopenia (narrow)
Renal	Renal failure	SMQ Acute renal failure (narrow)
	Proteinuria	SMQ Proteinuria (narrow)
	Glomerulonephritis (broad)	SMQ Chronic kidney disease (broad)
	Glomerulonephritis (narrow) Urinary tract infection	HLT Glomerulonephritis and nephrotic syndrome BICMQ Urinary tract infection (broad)

Table 7.8.1.4:1 Adverse events by system and safety topic using aggregated terms (cont'd)

System	Safety Topic	Definition (selection criteria)
Psychiatric	Depression	SMQ Depression (excl suicide and self-injury) (narrow)
	Suicide	SMQ Suicide/self-injury (narrow)
Cutaneous	Rash	BICMQ Skin rash (narrow): Exfoliative rash Mucocutaneous rash Rash Rash erythematous Rash follicular Rash generalized Rash macular Rash maculo-papular Rash maculovesicular Rash morbilliform Rash neonatal Rash papular Rash papulosquamous Rash pruritic Rash pustular Rash rubelliform Rash scarlatiniform Rash vesicular Symmetrical drug-related intertriginous and flexural exanthema Vascular access site bruising
	Pruritus	PT Pruritus
	Severe skin reactions	SMQ Severe cutaneous adverse reactions (narrow)

Table 7.8.1.4:1 Adverse events by system and safety topic using aggregated terms (cont'd)

System	Safety Topic	Definition (selection criteria)
Liver laboratories	Hepatic enzyme increased	Alanine aminotransferase abnormal Alanine aminotransferase increased Aspartate aminotransferase abnormal Aspartate aminotransferase increased Hepatic enzyme abnormal Hepatic enzyme increased Hepatic function abnormal Hypertransaminasaemia Liver function test abnormal Transaminases abnormal Transaminases increased Blood alkaline phosphatase abnormal Blood alkaline phosphatase increased Gamma-glutamyltransferase abnormal Gamma-glutamyltransferase increased
	Hyperbilirubinaemia	Blood bilirubin abnormal Blood bilirubin increased Blood bilirubin unconjugated increased Hyperbilirubinaemia Icterus index increased Jaundice Jaundice hepatocellular Bilirubin conjugated abnormal Bilirubin conjugated increased
	Alanine aminotransferase increased	Alanine aminotransferase increased Alanine aminotransferase abnormal
	Aspartate aminotransferase increased	Aspartate aminotransferase increased Aspartate aminotransferase abnormal
	Gamma-glutamyl-transferase increased	Gamma-glutamyltransferase increased Gamma-glutamyltransferase abnormal
	Blood alkaline phosphatase increased	Blood alkaline phosphatase increased Blood alkaline phosphatase abnormal

These definitions are based on MedDRA Version 21.0. Note that changes to these definitions due to MedDRA updates will not trigger a TSAP update. Updated definitions are maintained in BIRDS under Human Pharma/nintedanib/Clinical/substance level/Project Data Management and Statistics/Section 4 Database.

The most recent version effective at DBL date will be used for trial reporting.

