9.6 LIST OF POTENTIAL TERMS FOR HEPATIC INJURY DERIVATION

Table 9.6: 1 shows the list of potentially relevant MedDRA preferred terms to support the derivation of a potential hepatic injury:

Table 9.6: 1 List of potentially relevant MedDRA preferred terms

Symptom	MedDRA
Vomiting	PT Vomiting
Fatigue	PT Fatigue
Nausea	PT Nausea
Right upper abdominal quadrant pain or tenderness	HLT "Gastrointestinal and abdominal pains (excl oral and throat)"
Fever	PT Fever
Rash	BlcMQ skin rash (narrow)

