Anastomotic haemorrhage
Anastomotic ulcer haemorrhage
Bloody peritoneal effluent
Cullen's sign
Gastrointestinal vascular malformation haemorrhagic
Grey Turner's sign
Haemorrhagic ascites
Haemorrhagic hepatic cyst
Hepatic haematoma
Hepatic haemorrhage
Intestinal haematoma
Intestinal haemorrhage
Intestinal varices haemorrhage
Mesenteric haematoma
Mesenteric haemorrhage
Mucosal haemorrhage
Neonatal gastrointestinal haemorrhage
Peritoneal haematoma
Peritoneal haemorrhage

GI Oral:

Angina bullosa haemorrhagica
Gingival bleeding
Mouth haemorrhage
Oral contusion
Oral mucosa haematoma
Pharyngeal haematoma
Pharyngeal haemorrhage
Stomatitis haemorrhagic
Tongue haematoma
Tongue haemorrhage
Tonsillar haemorrhage
Tooth pulp haemorrhage
Tooth socket haemorrhage

GI Upper:

Chronic gastrointestinal bleeding

Duodenal ulcer haemorrhage
Duodenitis haemorrhagic
Gastric haemorrhage
Gastric ulcer haemorrhage
Gastric ulcer haemorrhage, obstructive
Gastric varices haemorrhage
Gastritis alcoholic haemorrhagic
Gastritis haemorrhagic
Gastroduodenal haemorrhage
Gastroduodenitis haemorrhagic
Gastrointestinal angiodysplasia haemorrhagic
Gastrointestinal haemorrhage
Gastrointestinal polyp haemorrhage
Gastrointestinal ulcer haemorrhage
Haematemesis
Haemorrhagic erosive gastritis
Haemorrhagic necrotic pancreatitis
Mallory-Weiss syndrome
Oesophageal haemorrhage
Oesophageal intramural haematoma
Oesophageal ulcer haemorrhage
Oesophageal varices haemorrhage
Oesophagitis haemorrhagic
Pancreatic haemorrhage
Pancreatitis haemorrhagic
Peptic ulcer haemorrhage
Small intestinal haemorrhage
Small intestinal ulcer haemorrhage
Ulcer haemorrhage
Upper gastrointestinal haemorrhage

Respiratory:

Bronchial haemorrhage
Bronchial varices haemorrhage
Epistaxis
Haemoptysis
Haemothorax
Laryngeal haematoma
Laryngeal haemorrhage
Nasal septum haematoma
Paranasal sinus haematoma
Paranasal sinus haemorrhage
Pulmonary alveolar haemorrhage
Pulmonary contusion
Pulmonary haematoma

Pulmonary haemorrhage
Respiratory tract haemorrhage
Respiratory tract haemorrhage neonatal
Thoracic haemorrhage
Tracheal haemorrhage
Traumatic haemothorax

Skin:

Abdominal wall haematoma
Abdominal wall haemorrhage
Achenbach syndrome
Administration site bruise
Administration site haematoma
Administration site haemorrhage
Application site bruise
Application site haematoma
Application site haemorrhage
Application site purpura
Bleeding varicose vein
Blood blister
Breast haematoma
Chest wall haematoma
Chronic pigmented purpura
Contusion

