Ecchymosis
Eyelid bleeding
Eyelid contusion
Eyelid haematoma
Haemorrhage subcutaneous
Haemorrhage subepidermal
Haemorrhagic urticaria
Henoch-Schonlein purpura
Immune thrombocytopenic purpura
Implant site bruising
Implant site haematoma
Implant site haemorrhage
Incision site haematoma
Incision site haemorrhage
Increased tendency to bruise
Infusion site bruising
Infusion site haematoma
Infusion site haemorrhage
Injection site bruising
Injection site haematoma
Injection site haemorrhage

Instillation site bruise
Instillation site haematoma
Instillation site haemorrhage
Lip haematoma
Lip haemorrhage
Medical device site bruise
Medical device site haematoma
Medical device site haemorrhage
Mucocutaneous haemorrhage
Muscle contusion
Muscle haemorrhage
Naevus haemorrhage
Nail bed bleeding
Palpable purpura
Petechiae
Post procedural contusion
Post procedural haematoma
Post procedural haematuria
Post procedural haemorrhage
Post transfusion purpura
Post-traumatic punctate intraepidermal haemorrhage
Puncture site haemorrhage
Purpura
Purpura fulminans
Purpura neonatal
Purpura non-thrombocytopenic
Purpura senile
Skin haemorrhage
Skin neoplasm bleeding
Skin ulcer haemorrhage
Splinter haemorrhages
Subcutaneous haematoma
Thrombocytopenic purpura
Thrombotic thrombocytopenic purpura
Traumatic haematoma
Traumatic haemorrhage
Umbilical haematoma
Umbilical haemorrhage
Vaccination site bruising
Vaccination site haematoma
Vaccination site haemorrhage
Varicose vein ruptured
Vascular access site bruising
Vascular access site haematoma
Vascular access site haemorrhage
Vascular access site rupture

Vascular graft haemorrhage
Vascular pseudoaneurysm ruptured
Vascular purpura
Vessel puncture site bruise
Vessel puncture site haematoma
Vessel puncture site haemorrhage
Wound haematoma
Wound haemorrhage

Urogenital:

Bladder tamponade
Blood urine
Blood urine present
Broad ligament haematoma
Cervix haematoma uterine
Cervix haemorrhage uterine
Coital bleeding
Cystitis haemorrhagic
Dysfunctional uterine bleeding
Genital contusion
Genital haemorrhage
Haematosalpinx
Haematospermia
Haematuria
Haematuria traumatic
Haemorrhage urinary tract
Haemorrhagic ovarian cyst
Intrapartum haemorrhage
Kidney contusion
Menometrorrhagia
Menorrhagia
Metrorrhagia
Nephritis haemorrhagic
Ovarian haematoma
Ovarian haemorrhage
Pelvic haematoma
Pelvic haematoma obstetric
Pelvic haemorrhage
Penile contusion
Penile haematoma
Penile haemorrhage
Perineal haematoma
Peripartum haemorrhage
Perirenal haematoma
Polymenorrhagia

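### SAP safety term lists misplace two preferred terms (a bruise under Rash, one haematuria term under Skin bleeding), and adjudicated deaths carry two sets of category names

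*SAP*

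**What the plan says.** **Rash.** SAP 7.8.1.4, Table 7.8.1.4:1, defines the Cutaneous topic Rash by a sponsor-customised query and prints its terms. The last two read "Symmetrical drug-related intertriginous and flexural exanthema Vascular access site bruising".

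**Bleeding.** SAP 9.8 allocates preferred terms to bleeding subcategories. Its Skin list contains "Vascular access site bruising" and also "Post procedural haematuria". Its Urogenital list contains Haematuria, Haematuria traumatic, Blood urine and Blood urine present.

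**Hepatic injury.** SAP 5.4.4 summarises the proportion of patients with signs of hepatic injury under five criteria. The fifth is ALT and/or AST at or above 3 times ULN together with one of a set of symptoms, rash among them, within 7 days either side of the laboratory result. SAP 9.6 gives the terms for those symptoms and maps rash to "BlcMQ skin rash (narrow", the query used in Table 7.8.1.4:1. It introduces the table as a "list of potentially relevant MedDRA preferred terms to support the derivation of a potential hepatic injury".

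**Deaths.** SAP 7.8.1.3 first says the committee assigns each death to one of four causes: cardiovascular, respiratory, neither of those, or undetermined. The next paragraph tabulates deaths by "adjudicated cause of death (Cardiac, Respiratory, Non-cardiac/non-respiratory or Undetermined". Protocol 3.1.1 also speaks of cardiac or respiratory causes.

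**The concern.** Bleeding, thromboembolism and liver injury are named risks of the drug (Protocol 1.2 and 2.3), so the lists that define these topics should put each event under the heading a reader expects.

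A bruise where a vessel was accessed is not a rash. Left in the rash query, it inflates the rash count. Because SAP 9.6 borrows that query, it can also enter a derived liver-safety variable with which it has no connection. A haematuria term under Skin moves a urinary bleed into the wrong subcategory. A death table whose row names differ from the committee's categories leaves the programmer to decide where a fatal vascular event goes.

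All safety analysis in this trial is descriptive (Protocol 7.3.4), so the tables are the safety result. The topic groupings also feed the drug-related and serious-event tables (SAP 7.8.1.4), the subgroup tables (SAP 7.4.3) and the whole-trial rates (SAP 7.8.1.6).

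**Working it through.** No arithmetic beyond a count applies. The check sets the lists side by side.

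**1. The bruise term**

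- Rash list (Table 7.8.1.4:1): 18 entries name a rash, 1 names an exanthema and 1 names a bruise, 18 + 1 + 1 = 20 in all. The bruise is the only entry that is not an eruption.
- The list is alphabetical and the bruise term sits in its alphabetical place at the end. A stray line from PDF extraction is therefore unlikely.
- SAP 9.8 lists the same term under Skin bleeding, next to the haematoma, haemorrhage and rupture terms for the same site. The SAP itself treats it as bleeding.

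**2. How it reaches hepatic injury**

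- SAP 9.6 maps the symptom rash to the same query, so the bruise term comes with it.
- Under SAP 5.4.4 the symptom counts only with ALT and/or AST at or above 3 times ULN, and only within 7 days either side of that result.
- A false derived case therefore needs all of the following: this exact preferred term, that laboratory result, that window, no other listed symptom in the window, and none of the other four criteria met.
- SAP 9.6 calls its entries potentially relevant and supportive. A match could supply the symptom; the text does not say that every match automatically makes a case.

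**3. The haematuria term**

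| Preferred term | Subcategory in SAP 9.8 |
|---|---|
| Post procedural haematuria | Skin |
| Haematuria | Urogenital |
| Haematuria traumatic | Urogenital |
| Blood urine | Urogenital |
| Blood urine present | Urogenital |

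One term departs from the pattern. It stands among the other post-procedural bleeding terms in the Skin list, which suggests that it was sorted by its first words and not by site.

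**4. The death categories (SAP 7.8.1.3)**

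| Assigned by the committee | Row in the table |
|---|---|
| Cardiovascular | Cardiac |
| Respiratory | Respiratory |
| Neither cardiovascular nor respiratory | Neither cardiac nor respiratory |
| Undetermined | Undetermined |

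The two sets pair one to one, but the first and third pairs differ in meaning and no mapping is given. The SAP's own MACE definition (Table 7.8.1.4:1) includes fatal vascular-disorder events and fatal strokes. Such a death could be adjudicated as cardiovascular. Read as shorthand, it goes in the Cardiac row; read literally, it goes in the third.

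**5. What stays the same**

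- Total bleeding is displayed from the standard haemorrhage query before the split into subcategories.
- Total deaths do not depend on row labels.
- Hepatic injury as an adverse event of special interest is taken from investigator reports (SAP 7.8.1.1), and the hepatic alert in Protocol 5.3.7.1 does not use these lists.
- No efficacy analysis uses them.

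**The case against.** **Visibility.** The grouped tables show preferred terms, and full tables by system organ class and preferred term are also produced (SAP 7.8.1, 7.8.1.4). A reader can see a misplaced term and re-sort it. This stands, and it is a main reason the point is minor. It helps less for the derived hepatic-injury proportion in SAP 5.4.4, for which no breakdown by preferred term is described.

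**Updates outside the SAP.** The definitions may be maintained outside the document, and the version effective at database lock is used. For Table 7.8.1.4:1 the clause concerns changes caused by MedDRA updates, and SAP 9.8 refers back to the same arrangement. A misplaced term or a mismatched label is not such a change, so this route would not necessarily correct it.

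**Stronger readings a reader might infer**

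- *That a bruise by itself signals hepatic injury.* It does not; the enzyme elevation and the time window are both required.
- *That haematuria in general is counted as skin bleeding.* Only one term is affected.
- *That one event under two topics is an error in itself.* The table overlaps by design: pulmonary embolism with venous thromboembolism, and ALT increased with hepatic enzyme increased. Immune thrombocytopenic purpura is in both Thrombocytopenia and Skin bleeding. The fault is the presence of a bruise in Rash.
- *That cardiovascular deaths will be miscounted.* This is not shown. The labels pair one to one, the table is said to show the adjudicated cause, and no second classification is described. Shorthand labelling is the natural reading.
- *That gastrointestinal bleeding without a stated site is wrongly put under GI Upper.* Gastrointestinal haemorrhage is under GI Upper while "Neonatal gastrointestinal haemorrhage" is under GI Nonspecific, which looks uneven. But the SAP states no rule that a term naming no site must be nonspecific, and the neonatal term should not arise in patients aged 18 or over. This is largely a convention that the SAP leaves unstated.

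**Conclusion.** Wrong as written, and minor. Two preferred terms are misplaced: the bruise term in Rash, which also enters the symptom list for derived hepatic injury, and one haematuria term under Skin bleeding. The cause-of-death table uses row names that do not match the committee's categories.

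The effect is confined to descriptive safety tables: the rash count, derived hepatic injury by symptom, the skin/urogenital bleeding split and the cause-of-death labels. The documents give no event counts for these terms, so the number of affected patients cannot be stated. The conjunction of conditions needed for a false hepatic-injury case suggests it would be small.

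The conclusion assumes that the printed Rash list is what will be programmed and that the rash query named in SAP 9.6 is the one printed in Table 7.8.1.4:1.

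**What to change.** Before database lock:

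1. Remove Vascular access site bruising from the Rash grouping, and so from the rash symptom in Table 9.6:1. Keep it under Skin bleeding.
2. Move Post procedural haematuria from Skin to Urogenital in SAP 9.8.
3. In SAP 7.8.1.3, label the table rows with the four categories the committee assigns, and carry the same labels into the whole-trial version in SAP 7.8.1.6.
4. Optionally, state one rule for gastrointestinal bleeding terms that name no site and apply it to all of them. Moving Gastrointestinal haemorrhage alone would leave Chronic gastrointestinal bleeding, Gastrointestinal ulcer haemorrhage, Gastrointestinal polyp haemorrhage and Ulcer haemorrhage under GI Upper and recreate the unevenness.

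The cost is a few edits to term lists and table labels, with a line in the SAP history. No new data are needed and no model changes. The rash query is the sponsor's own, so the first edit is within the sponsor's control.
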